[figure not shown]

**NON-INTERVENTIONAL STUDY OF ADVANCED RENAL CELL CARCINOMA
TREATMENT PATTERNS AND UNMET NEEDS**

This document contains confidential information belonging to Pfizer. Except as otherwise agreed to in writing, by accepting or reviewing this document, you agree to hold this information in confidence and not copy or disclose it to others (except where required by applicable law) or use it for unauthorized purposes. In the event of any actual or suspected breach of this obligation, Pfizer must be promptly notified.

PFIZER CONFIDENTIAL

Title	Study of advanced renal cell carcinoma treatment patterns and unmet needs using real world claims and electronic medical record data.
Protocol number	A6181232
Protocol version identifier	01
Date of last version of protocol	4 October 2019
Research question and objectives	
The study aims to assess treatment patterns and outcomes in advanced RCC patients in real world clinical practices across various real world databases. Four databases will be evaluated: IBM's Truven MarketScan Commercial, Optum Clininformatics, the IMS PharMetrics claims databases and The PanTher (which has both Humedica EMR data including EMR notes linked to Optum claims).
 
The primary study objectives include:
 
Treatment patterns: Characterize first-line and subsequent lines of therapy. Treatment patterns will be summarized for the following therapy regimens:
• immuno-oncology (IO) monotherapy;• IO+IO combo-therapy;• IO+tyrosine kinase inhibitor (TKI) combo-therapy;• TKI monotherapy;• Other.Analyze Cohorts of Interest: To describe patient demographics and clinical characteristics, and select outcomes of interest among the following first-line advanced RCC cohorts of interest:
• immuno-oncology (IO) monotherapy;• IO+IO combo-therapy;• IO+tyrosine kinase inhibitor (TKI) combo-therapy;• TKI monotherapy;• Other.

PFIZER CONFIDENTIAL

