6.1. Study Design

Patients receiving aRCC treatment (see [Table 4](#)), between April 2018 and the present, who have no prior aRCC treatment in their claims history will be identified for this study. The index date for each analysis will be defined as the date of initiation of the aRCC treatment. Patients must have at least 2 RCC diagnoses at least 30 days apart to be included. Patients must also have 2 secondary malignancy ICD9 or ICD10 codes (often used in claims data to suggest cancer metastases) at least 30 days apart in the 12 months pre and one month post index aRCC treatment. [CCI](#)

Various algorithms and temporal relationships between the secondary malignancy codes, RCC diagnosis codes and other cancer codes were explored toward developing the criteria for metastatic advanced RCC for this study.

Study will require a minimum of 12 months of enrollment prior to the index date. Feasibility was assessed for various lengths of continuous enrollment criteria (3, 6 and 12 months post index date) toward understanding sample sizes available for analysis and follow-up periods. Study outcomes will be assessed for three patient cohorts (3, 6 and 12 month cohorts) according to their available months of continuous enrollment.

PFIZER CONFIDENTIAL

First line therapy cohorts will first be presented for all patients regardless of follow-up time available. Baseline characteristics, costs and utilization will be measured over the 6 months prior to the index date. Duration of therapy and utilization analysis will require at least 6 months of post-index enrollment, with sub-analysis preformed on the cohorts with 3-months and 12-months of post-index enrollment. Utilization and cost will be performed per-utilizer-per-month (PUPM), and then separately for each of the cohorts with 3-month, 6-month and 12-months of post-index enrollment.

The analysis will focus on, but is not limited to, the following regimens:

- a. **Combo IO:** nivolumab combined with ipilimumab;
- b. **Monotherapy TKI:** sunitinib, cabozantinib, and pazopanib;
- c. **Combo TKI + IO:** avelumab in combination with axitinib, pembrolizumab in combination with axitinib;
- d. **Other:** all others regimens.

PFIZER CONFIDENTIAL

[figure not shown]
[figure not shown]
[figure not shown]

Figure 1: Cohort Identification

Analysis 1. Treatment Patterns and Duration

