Treated Period Follow-Up. Patients will be followed over the period treated with advanced RCC therapy. Time treated will be defined as the time from the index date to the date of the end of the last advanced metastatic RCC prescription (end of supply for orals/administration date plus 30 days for injectables), end of enrollment, end of follow up, or death (see more specifics on oral versus injectable rules in [6.3.1 Variables](#) section of this protocol).

Analysis 2. Describe various treated populations of interest by demographics, clinical characteristics, as well as cost and utilization

Describe the demographics and other baseline characteristics of the first-line treated cohorts of interest identified in the treatment patterns analysis (Analysis 1) for RCC patient as follows:

Baseline Characteristics (see [6.3.2 Baseline Characteristics](#)):

- Age at index;
- Gender;
- Race;
- Region;

PFIZER CONFIDENTIAL

- Payor;
- Clinical characteristics: Quan-Charlson Comorbidity Index (CCI) scores and baseline comorbidities;
- Prior treatment (6 months prior) - nephrectomy, radiation/ablation, interferon, high-dose interleukin-2, other anti-neoplastic medications;
- Secondary malignancy locations (6 months prior);
- Baseline costs of care (6 months prior);
- Baseline health care resource utilization (6 months prior).

Analysis 3: Evaluate the key outcomes of interest for advanced RCC therapy regimens toward demonstrating existing unmet needs in RCC given currently available therapies (eg, ipilimumab/nivolumab).

Treatment duration, discontinuation, interruption, switching and therapy augmentation will be presented, as will the burden of disease costs and health care utilization. Survival will also be explored, although regimens are too new for extensive follow-up time.

Overall Outcomes Study Period. For the outcomes analysis, follow-up will be defined as the time from the index date to the end of specified follow up period of 6 months, end of enrollment, or death. Follow-up may vary given sample sizes of study population, with by subanalysis using 1-year or 2-years of follow-up time from study index date for certain sub-populations.

Outcomes include:

- **Time to Treatment Failure (TTF)** – First line time to treatment failure (TTF) is defined as the time from first-line therapy start to treatment discontinuation for any reason, including switched, augmented therapy, end of enrollment, death.

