6.2.1. Inclusion Criteria

Subjects will be selected irrespective of their survival status. Patients must meet all of the following inclusion criteria to be eligible for inclusion in the study:

- **Index date:** The first prescription or administration of one of the medications indicated for advanced RCC recorded in the database between April 2018-March 31, 2019, among those with no aRCC treatment in their history.
- Age 18 years or older in the year of the index first line therapy prescription.
- 2 or more RCC diagnoses (ICD-9: 189.0; ICD-10: C64.1, C64.2, C64.9) at least 30 days apart, in the 1 year prior to the index date until 30 days post index date.

PFIZER CONFIDENTIAL

- 2 or more code for secondary malignancy codes indicating possible diagnoses for metastatic disease at least 30 days apart, in the 1 year prior to the index date until 30 days post index date. (ICD-9: xx-199.xx; ICD-10: C77-C79, except ICD9: 198.0 Secondary malignant neoplasm of the kidney and ICD10: C79.0 Secondary malignant neoplasm of the kidney and renal pelvis).
 - CCI [REDACTED]
- Continuous enrollment from 12 months prior to the index date. Patients will be required to have continuous enrollment from their index date until the end of the available data. This will allow for sub-analysis of cohorts with 3 months, 6 months and 12 months of available data.

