Medical claims or encounter data are collected from all available health care sites (inpatient hospital, outpatient hospital, emergency room, physician's office, surgery center, etc.) for virtually all types of provided services, including specialty, preventive and office-based treatments. Medical claims and coding conform to insurance industry standards. Claims for ambulatory services submitted by individual providers, eg, physicians, use the HCFA-1500 format. Claims for facility services submitted by institutions, eg, hospitals, use the UB-82 or UB-92 format. Medical claims include: multiple diagnosis codes recorded with the ICD-9-CM diagnosis codes; procedures recorded with ICD-9-CM procedure codes, Current Procedural Terminology (CPT), or Health Care Financing Agency (HCFA) Common Procedure Coding System (HCPCS) codes; site of service codes; provider specialty codes; revenue codes (for facilities); paid amounts; and other information. Typically, facility claims do not include any drugs administered in hospital. Approximately 6-9 months following the delivery of services is required for complete medical data, therefore patients will be followed for this additional time period. In summary, the analysis window will include data from 24 months pre index date, and 24 months post index date.

PFIZER CONFIDENTIAL

Integrated Optum E.H.R and Claims (PanTher)

Integrated Optum E.H.R. (formerly Humedica) clinical data and Optum Clininformatics administrative claims data (United enrollees) are included in the Optum PanTher Database. Estimated to be approximately 15% of the Optum Claims lives are represented in this database. This asset combines the clinical specificity of the Optum E.H.R. data with the administrative claims data which includes cost data, pharmacy fill data, and enrollment time periods among other things.

The Optum EHR database has broad geographic representation and includes patient demographic and clinical information, including diagnosis, medications, labs, procedures, microbiology and biomarkers. Optum EHR also extracts data from physician notes using industry-leading Natural Language Processing (NLP).

[figure not shown]

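### No data cut-off is stated and the post-index windows conflict, so cohorts defined by enrollment can take in immature medical claims and understate costs, utilization and infusion exposure

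*Combined protocol and SAP*

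**What the plan says.** **Windows.** Section 6.4 (Optum Clininformatics) states that "the analysis window will include data from 24 months pre index date, and 24 months post index date". Section 6.1, Analysis 3, ends outcome follow-up at 6 months. It allows follow-up to vary with sample size, "with by subanalysis using 1-year or 2-years of follow-up time from study index date for certain sub-populations". Section 6.1 also defines 3-, 6- and 12-month cohorts by months of continuous enrollment, and those are the only lengths for which it reports a feasibility assessment.

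**Index dates.** Section 6.2.1 takes first treatments "recorded in the database between April 2018-March 31, 2019". Section 6.1 takes patients treated "between April 2018 and the present, who have no prior aRCC treatment in their claims history", which has no fixed end.

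**Calendar anchor.** The title table dates the protocol "4 October 2019". No section gives a data cut-off or extract date. Section 6.6 foresees periodic regeneration of tables as databases refresh. The opening of Section 6.4 leaves sub-analyses to a later amendment, once population sizes are known.

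**Claims lag (Section 6.4).**
- Optum medical: "Approximately 6-9 months following the delivery of services is required for complete medical data, therefore patients will be followed for this additional time period".
- Optum pharmacy: typically within 6 weeks.
- Standard MarketScan: about six months after a quarter or year closes.
- MarketScan Early View: 90 days, holding about 85% of office visits and 70% of hospital claims.
- PharMetrics: 4-6 months.

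**Handling of the lag.** Section 6.2.1 runs required enrollment to the last available data and subtracts no lag. The MarketScan text accepts Early View and waives full adjudication, because the study is said to concern comorbidities and treatments around the start of glasdegib. Section 6.7 keeps patients with no reported costs in the denominator at zero.

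**The concern.** A cohort defined by enrollment shows that a patient was covered for 3, 6 or 12 months. It does not show that the claims for those months have reached the database. With no stated cut-off and no lag removed, the last months before an extract count fully in the denominator while part of their medical claims is missing from the numerator. Under the zero-cost rule, a claim that has not yet arrived is treated as care that did not happen.

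The glasdegib rationale does not fit this study. Glasdegib is not among the medications in Table 4, and cost and utilization after index are stated outcomes.

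The error need not be equal across regimens. Oral TKIs are seen through pharmacy claims, which arrive in Optum within about 6 weeks. Table 4 lists the IO drugs as injections. To the extent that these are billed as medical claims (an assumption), they face the 6-9 month lag. An infusion claim still in process can look like a gap of more than 30 days, which the plan classes as discontinuation or interruption. Regimen descriptions of duration and cost could then differ because of claims timing alone.

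The conflicting windows make this worse, because a programmer cannot tell which horizon is intended at which refresh.

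**Working it through.** **Inputs.** Index window 1 April 2018 to 31 March 2019, 365 days (Section 6.2.1, with April taken as 1 April). Lags as listed in Section 6.4. Assumptions: extract on 4 October 2019; index dates spread evenly; no deaths or disenrollment, so the shares are upper bounds.

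**The plan's figure.** The 24-month post-index window cannot be reproduced at the protocol date. From 1 April 2018 to 4 October 2019 is 551 days, and 551 / 30.4375 = 18.1 months for the earliest possible patient. From 31 March 2019 it is 187 days, or 6.1 months.

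**Formula.** Data end E = extract date - lag. Share with h complete months = (number of index days d with d + h months on or before E) / 365.

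| Source and lag | E | 6 months | 12 months | 24 months |
|---|---|---|---|---|
| No lag | 4 Oct 2019 | 365/365 = 100% | 187/365 = 51.2% | 0% |
| Optum pharmacy, 6 weeks | 23 Aug 2019 | 329/365 = 90.1% | 145/365 = 39.7% | 0% |
| MarketScan Early View, 90 days (incomplete) | 6 Jul 2019 | 281/365 = 77.0% | 97/365 = 26.6% | 0% |
| PharMetrics, 4 months | 4 Jun 2019 | 248/365 = 67.9% | 65/365 = 17.8% | 0% |
| PharMetrics or Optum medical, 6 months | 4 Apr 2019 | 187/365 = 51.2% | 4/365 = 1.1% | 0% |
| Standard MarketScan, last quarter closed six months earlier | 31 Mar 2019 | 183/365 = 50.1% | 0% | 0% |
| Optum medical, 9 months | 4 Jan 2019 | 95/365 = 26.0% | 0% | 0% |

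**Later extracts, Optum medical claims (6-month lag / 9-month lag).**
- 4 April 2020: 12 months 51.2% / 26.0%; 24 months 0% / 0%.
- 4 July 2020, nine months after the protocol date: E is 4 January 2020 / 4 October 2019. For 12 months, 279/365 = 76.4% / 187/365 = 51.2%. For 24 months, 0% / 0%, because the first patient's 24 months end on 1 April 2020.
- 4 October 2020: 12 months 100% / 76.4%; 24 months 1.1% / 0%.
- 4 April 2021: 12 months 100% / 100%; 24 months 51.2% / 26.0%.

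**Dates for full coverage.** The last index date plus 12 months is 31 March 2020; adding 6-9 months gives an extract between 30 September and 31 December 2020. For 24 months the corresponding dates are 30 September to 31 December 2021.

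**Open-ended index window.** Under the Section 6.1 wording, later starters join the denominator. At a given extract the shares would then be no higher than those above, and no extract would cover the whole window.

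**Size of the shortfall.** Section 6.4 quantifies it only for Early View: about 100 - 70 = 30% of hospital claims and 100 - 85 = 15% of office visits absent. Completeness by month is not given for the other sources, so the bias in dollars or visits cannot be calculated.

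**The case against.** The strongest reply is that the extract date above is assumed. The protocol date is not a data cut-off. Section 6.6 expects refreshes, Section 6.4 adds time for the lag, and sub-analyses await an amendment. That stands. A reader might infer that the 24-month and 12-month analyses will be empty. The documents do not support this; they show only that these horizons were out of reach, or largely incomplete for medical claims, until a later extract that the plan does not name.

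Three further points also stand.
- The 2-year sub-analysis is conditional on sample size and sub-population, and Section 5 concedes that the regimens are too new for long follow-up. Only the Section 6.4 sentence is unconditional. Even that might describe the bounds of the data pull, since its 24 months before index also exceed the 12 months of required enrollment.
- A reader might infer that following patients for 6-9 more months cannot help, because it only adds newer immature claims. For a fixed horizon this is wrong: the wait lets claims inside the horizon mature. The Section 6.4 remedy is vague rather than mistaken.
- The 6-9 month lag is Optum's and should not be applied to every source. The 12-month share is 17.8% for PharMetrics at 4 months and 39.7% for Optum pharmacy claims.

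Counting patients without costs as zero is also reasonable when claims are complete, and Kaplan-Meier methods accommodate unequal follow-up. Neither helps when claims are missing inside time that is counted as observed. Nothing in the enrollment rules prevents that.

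**Conclusion.** The point holds as a gap in the data rules, together with windows that must be reconciled. At an assumed extract on the protocol date:
- no patient has 24 months (maximum 18.1);
- 12 complete months of medical claims exist for 0-1.1% of index dates in Optum and 0% in standard MarketScan, and 12 complete months of claims for 1-18% in PharMetrics;
- the main 6-month horizon is complete for only 26-51% of index dates in Optum medical claims.

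These shares rest on even index dates and no attrition, and they improve with later extracts.

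The conclusion on bias does not depend on one particular extract date. At any extract taken before claims have matured over the horizon, cohort entry by enrollment, acceptance of Early View and the zero-cost rule together push recent medical costs, utilization and infusion exposure downward. The direction is clear; the size is not calculable from the documents. A greater effect on infused than on oral regimens is plausible but depends on how the infusions are billed.

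**What to change.** 1. For each database, state the extract date. End follow-up for outcomes based on medical claims at that date minus the database's own lag: Optum 6-9 months, standard MarketScan about six months after period close, PharMetrics 4-6 months.
2. Admit a patient to the 3-, 6- or 12-month cohort for cost, utilization or infusion duration only if indexed at least that long before the resulting date.
3. In Section 6.4, delete the glasdegib sentence and do not use Early View for cost and utilization outcomes.
4. Reconcile Sections 6.1, 6.2.1 and 6.4, including the end of the index window. Either remove the 24-month post-index window and the 2-year sub-analysis, or make both conditional on an extract with complete claims covering them.
5. Report the number of patients and the index-date range beside each horizon.

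The cost is a few sentences and one date filter per database. The 12-month cohorts will be smaller or later, and MarketScan cost results lose their most recent months. Waiting until the whole index window is covered is optional, provided that item 5 is reported.

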- **% continuing** – those with no gap in therapy greater than 30 days and who do not begin a new treatment during the study period.
- **% discontinuing** – those with gap in therapy greater than 30 days and who do not begin a new treatment.
- **% with treatment interruption** - those with gap in therapy greater than 30 days but who eventually continue the original treatment (have an additional administration or refill) and do not switch or augment therapy during the study period.
- **% switching** – those with gap in therapy greater than 30 days and who begin a new treatment.
- **% augmenting** – those who begin a new treatment but continue using the original treatment (have an additional administration or refill) and do not have a gap in therapy greater than 30 days of their original treatment.
- **Overall and aRCC Follow-Up Costs:** Total and RCC-specific pharmacy, medical costs from aRCC therapy index through follow-up period (costs summarized as: mean, median costs per patient and costs per patient per month).

PFIZER CONFIDENTIAL

- **Overall and aRCC Follow-Up Utilization:** Total and RCC-specific inpatient, ER, outpatient visits from aRCC therapy index through follow-up period (utilization will be summarized as: mean, median utilization per patient and utilization per patient per month).
- **Overall landmark survival:** Using Optum claims and PanTher data, landmark survival will be described and compared over follow-up time periods (3, 6, 12 months).
- **Mean/Median Survival:** Using Optum claims and PanTher data median survival time will be described and compared over follow-up time periods determined after feasibility assessments of cohorts of interest.

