6.3.4. Cost and Utilization Variables

[figure not shown]
Table 8. Cost and Utilization Variables

Variable	Operational definition

All-cause Health Resource Utilization: Total inpatient, ER, outpatient visits from index aROC period.
	
Any healthcare resource use per patient per month (PPPM) will be examined for each regimen-based cohort under each LOT and will further be categorized as the following:
 
Occurrence of (Categorical: Yes/No):
 
• any inpatient stay;• any outpatient visit;• any ER visit. 
Number of visits (Continuous):
 
• inpatient stays;• outpatient visits;• ER visits. 
Inpatient LOS (Continuous: days).

PFIZER CONFIDENTIAL

Variable	Operational definition

aRCC HR Utilization:
 
RCC-specific inpatient, ER, outpatient visits from aRCC therapy index through follow-up period.
	
RCC-related healthcare resource use per patient per month (PPPM) will be examined for each regimen-based under each LOT.
 
Medical claims will be considered RCC-related if they have an ICD-9/10-CM diagnosis code for RCC in any position on the claim.
 
Occurrence of (Categorical: Yes/No):
 
• any inpatient stay;• any outpatient visit;• any ER visit. 
Number of visits (Continuous):
 
• inpatient stays;• outpatient visits;• ER visits. 
Inpatient LOS (Continuous: days).

PFIZER CONFIDENTIAL

Variable	Operational definition
All-cause Healthcare Costs Overall medical costs and pharmacy costs from aRCC therapy index through follow-up.	
Continuous: dollars
 
All-cause healthcare costs will be examined for each regimen-based cohort under each LOT. Costs will be adjusted to 2019 US dollars (USD) using the medical care component of the Consumer Price Index (CPI). Health care costs PPPM will be provided, and will be further categorized as:
 
• Inpatient stay costs;• Outpatient costs;• ER visit costs;• Pharmacy costs (medical);• Pharmacy costs (pharmacy);• Total costs.

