The Optum EHR database includes patient records from multiple EMR systems which capture data from different sites of care and a full spectrum of inpatient and outpatient treatment (eg, both Written Prescription and Inpatient-Administered medications). Records are completely de-identified and are fully compliant with the Health Insurance Portability and Accountability Act (HIPAA). Data is sourced from large Integrated Delivery Networks (IDN) with over 60% of patients having both outpatient and hospital information. The remainder of the patients are from large multi-specialty physician practices.

Outpatient laboratory test results are available for subpopulations of the research database. Standard Logical Observation Identifiers Names and Codes (LOINC) coding is used to define specific tests and results. Test results data can be linked to the other health care utilization and pharmacy claims data in the research database. Results included in the database are typically from blood-based tests (eg, low-density lipoprotein, glycated hemoglobin levels) that are sent for processing to two of the largest laboratory facilities in the country. Data are available for approximately 30-40% of members who were administered the test, depending on the test.

Truven Marketscan Commercial:

The MarketScan data warehouse is a family of databases from commercially insured lives. Pfizer licenses the following data sources: healthcare claims, hospital drug/discharge information with links to claims data and Medicare Supplemental files. The Truven Health MarketScan Research Databases reflects the combined healthcare service use of individuals covered by Truven Health clients (including employers, health plans, and hospitals) nationwide. Truven Health builds databases comprise the healthcare experience of the clients' covered populations, as well as information about the populations themselves and the providers that serve them. MarketScan Research Databases provide detailed cost, utilization, and outcomes data for healthcare services performed in both inpatient and outpatient settings. In the claims databases, the medical services are linked to outpatient prescription drug claims and person-level enrollment data using unique enrollee identifiers.

PFIZER CONFIDENTIAL

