The MarketScan Commercial Database contains the healthcare experience of privately insured individuals. Coverage is provided under a variety of fee-for-service, fully capitated, and partially capitated health plans, including preferred provider organizations, point of service plans, indemnity plans, and health maintenance organizations.

The Enrollment Detail Table provides a single record per month of enrollment for each enrollee, with detailed demographic information.

Claims are not included in the database until they have been adjudicated; there is a lag of approximately six months after the close of a calendar year or a quarter between services provided and their inclusion in the Research Databases. However, the Early View Database has a 90-day lag that includes paid amounts for 100 percent of prescription drugs, approximately 85 percent of physician office visits, and approximately 70 percent of hospital claims. The MarketScan Early View Database includes all of the components found in the standard MarketScan Commercial and Medicare Supplemental Databases. It includes standardized inpatient, outpatient, pharmaceutical, and health-plan enrollment data. The MarketScan Early View Database captures healthcare services incurred up to 90 days before data release and includes only adjudicated claims. However, the medical component of care for some patients will not be complete, since some claims (particularly inpatient claims) take longer to be adjudicated. Because this study is examining only comorbidities prior to and treatments during or prior to glasdegib initiation fully adjudicated claims are not required and all available data will be used including Commercial, Medicare Supplemental, and Early View Databases.

[figure not shown]
Pharmetrics Plus

The PharMetrics Plus database is comprised of fully adjudicated medical and pharmacy claims. Specifically, it contains a longitudinal view of inpatient and outpatient services, prescription and office/outpatient administered drugs, costs and enrollment information. With PharMetrics Plus, you can track an enrolled patient across all sites of care: hospital, specialist, emergency room, pharmacy, primary care, ambulatory, and more.

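### The MarketScan text waives fully adjudicated claims for a reason that does not apply to this study, and so lets incomplete Early View data into post-index cost and utilization

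*Combined protocol and SAP*

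**What the plan says.** The MarketScan part of Section 6.4 gives a lag of about six months after a quarter or year closes for the standard files and 90 days for Early View. It puts Early View at 100% of prescription drugs, "approximately 85 percent of physician office visits, and approximately 70 percent of hospital claims". It adds that "the medical component of care for some patients will not be complete, since some claims (particularly inpatient claims) take longer to be adjudicated". It then gives its reason for accepting this, "Because this study is examining only comorbidities prior to and treatments during or prior to glasdegib initiation fully adjudicated claims are not required", and its rule: "all available data will be used including Commercial, Medicare Supplemental, and Early View Databases".

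The outcomes are set elsewhere. Section 5 lists health care costs and utilization as objectives. Section 6.1 (Analysis 3) specifies "Total and RCC-specific inpatient, ER, outpatient visits from aRCC therapy index through follow-up period", with a parallel item for pharmacy and medical costs. Table 8 in Section 6.3.4 states "All-cause healthcare costs will be examined for each regimen-based cohort under each LOT", with inpatient, outpatient and ER components. On timing, Section 6.1 says that "follow-up will be defined as the time from the index date to the end of specified follow up period of 6 months", with cohorts of 3, 6 and 12 months. Only survival is limited to particular databases.

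**The concern.** The sentence appears to come from a study of another drug, but it is more than a stray name: it is the only justification given for an operative data rule. Changing the drug name would not repair it, because the claim that only prior comorbidities and treatments are examined is also untrue here.

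If the rule is followed as written, recent MarketScan follow-up enters the cost and utilization tables with claims missing. Section 6.7 counts patients without recorded costs as 0, so the loss lowers means without showing up as missing data. Section 6.4 also aims to replicate results across databases, and a difference in completeness could be read as a difference in care.

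**Working it through.** **1. Premise against study.** The sentence refers to glasdegib; Table 4 does not list it. The sentence says only prior comorbidities and treatments are examined; Sections 5, 6.1 and 6.3.4 measure medical cost and use from index onward. Both halves fail.

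**2. Loss in time covered only by Early View** (from the stated percentages)
- Hospital claims: observed = 0.70 × true, so true = 1/0.70 = 1.43 × observed.
- Office visits: observed = 0.85 × true, so true = 1/0.85 = 1.18 × observed.
- Prescription fills: complete.

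**3. Share of follow-up affected.** The plan gives no figure to reproduce, so this is an illustration.
- From the documents: index dates April 2018 to 31 March 2019 (Section 6.2.1); windows of 3, 6 and 12 months; lags as above; protocol date 4 October 2019.
- Assumed: release on the protocol date; one index patient per day over 365 days; windows of 91, 182 and 365 days; only windows that close by the end of Early View are counted.
- Early View ends 4 October 2019 − 90 days = 6 July 2019. With quarterly closes, the standard file ends 31 March 2019.

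Early View share = overhanging days / all window days:
- 3 months: 90 index dates overhang by 1 to 90 days; (90 × 91/2) / (365 × 91) = 4095/33215 = 0.123.
- 6 months: 281 windows close in time, 97 overhang; (97 × 98/2) / (281 × 182) = 4753/51142 = 0.093.
- 12 months: 98 windows close in time, 97 overhang; 4753 / (98 × 365) = 4753/35770 = 0.133.

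Two loss patterns bracket the result. Flat: 30% (hospital) or 15% (office) is missing throughout Early View time. Linear: that loss at 90 days of age falls to zero at 180 days, i.e. base × (180 − age)/90.

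| Release; standard file ends | Hospital flat, 3/6/12 mo | Hospital linear, 3/6/12 mo |
|---|---|---|
| 4 Oct 2019; 31 Mar 2019 | 3.70 / 2.79 / 3.99% | 0.99 / 0.82 / 1.17% |
| 4 Oct 2019; 31 Dec 2018 | 11.1 / 10.3 / 11.4% | 0.99 / 0.82 / 1.17% |
| 31 Mar 2020; 30 Sep 2019 | 0 / 0 / 1.30% | 0 / 0 / 0.41% |
| 30 Jun 2020; 31 Dec 2019 | 0 / 0 / 0.90% | 0 / 0 / 0.28% |
| 30 Sep 2020; 31 Mar 2020 | 0 / 0 / 0 | 0 / 0 / 0 |

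Office-visit losses are half of these: in the first row, 1.85/1.39/1.99% flat and 0.50/0.41/0.59% linear. The last row is zero because the 12-month window of a patient indexed on 31 March 2019 closes on 29 March 2020. It assumes quarterly closes. If files close only yearly, the standard file at that release ends 31 December 2019, and the 12-month flat bound is 0.90% (linear 0).

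**4. False treatment gaps.** A missing infusion claim can look like a gap. The number m of consecutive missed claims needed is the smallest with interval × (m + 1) − cover > 30.
- Cover of 30 days (Table 5, administration plus 30 days): m = 2, 2, 4, 8 for intervals of 28, 21, 14, 7 days.
- Cover equal to the interval (Table 9, imputed days supply): m = 2, 2, 3, 5.

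The two rules disagree for the 14- and 7-day intervals, and the plan does not say whether the 85% or the 70% figure applies to infusions. No reliable rate follows.

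**The case against.** The strongest reply is that later data remove the problem. The Optum part of Section 6.4 sets a window of 24 months after index and allows 6-9 months for medical data to complete. If that is study-wide, data for the last index date run to March 2021 and every 3-, 6- and 12-month window is complete. Section 6.6 also foresees periodic regeneration of tables. This stands as a possibility. But the allowance is written under Optum, the MarketScan text states the opposite rule, and neither place commits to a MarketScan release.

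The other databases also have recency limits (6-9 months for Optum, 4-6 months for PharMetrics), and replication is promised only as far as possible. So MarketScan is not unique in having a lag; it is the only one whose text expressly waives completeness.

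A reader might infer more than the documents support:
- *That 30% of hospital cost is lost.* That needs a whole window in Early View, and shares of claims are not shares of dollars.
- *That a contrast between immuno-oncology and TKI regimens is biased in a known direction, or that combinations are safe from false gaps.* Table 5 requires the gap to cover all agents, but with two injected drugs both claims may be missing together.
- *That Early View is unlicensed.* The licence text, "Pfizer licenses the following data sources: healthcare claims, hospital drug/discharge information with links to claims data and Medicare Supplemental files", is generic and settles nothing.
- *That unadjudicated amounts are used.* Early View holds only adjudicated claims; the defect is missing claims.

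**Conclusion.** The sentence is wrong as written, and nothing in the protocol clearly contains its effect for MarketScan. It should be corrected before the cost and utilization tables are run.

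The likely size is modest. With a release on the protocol date and a standard file to 31 March 2019, average shortfalls are about 1-4% for hospital claims and 0.4-2% for office visits. The 10-11% figure needs a standard file ending 31 December 2018 and flat loss, which treats some services more than six months old as still 30% missing; it is an upper bound. With a release at end-September 2020 or later and quarterly closes, the shortfall is zero in all three windows.

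These figures rest on the assumed release, uniform accrual and the Section 6.2.1 index window. Section 6.1 instead runs index dates to the present, which would keep placing the newest patients in Early View. The shortfall in dollars cannot be derived from the documents. False gaps for infused drugs are plausible but unquantified.

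**What to change.** 1. Delete the glasdegib sentence.
2. State that MarketScan post-index medical cost, utilization and infused-drug duration use only the standard Commercial and Medicare Supplemental files, or an explicit run-out of about six months, with follow-up for these outcomes ending at the last complete quarter.
3. Name the release. A standard file through 31 March 2020 would complete all 12-month windows for index dates to 31 March 2019.
4. Say whether the 24-month window and 6-9 month run-out written under Optum apply to MarketScan.
5. Keep Early View, if wanted, for oral-drug persistence or for a sensitivity analysis with and without it.

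The drafting cost is a few sentences. The real cost is time: under the six-month lag, complete 12-month MarketScan results wait until about September 2020, and the 2-year sub-analyses need a later file. Stopping at a file ending 31 March 2019 avoids the wait but leaves 275 of 365 index dates (75%) with a complete 3-month window, 184 (50%) with a complete 6-month window, and 1 (0.3%) with a complete 12-month window.
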